#### 10.4 Analysis of Vital Signs

Vital sign measurements of systolic and diastolic blood pressure, heart rate, resting respiratory rate and temperature will be summarized.

Each vital sign variable will be summarized for all time points (Baseline, Day 3, Day 6, Day 13, Month 3, and end of study follow-up) with the number of non-missing observations, mean and standard deviation, median, Q1, Q3, minimum, and maximum. Mean change from baseline to each applicable post-baseline visit will be summarized for each vital sign variable, with the number of observations, baseline mean, and visit mean. The change from baseline mean, standard error, and 95% confidence interval will be presented for the mean change from baseline within each treatment group and difference between treatment arms (A, B, C, D vs. E) and between all active arms and the control arm (A – D vs. E) using separate ANOVA models.

Vital signs variables will be evaluated based on potentially clinically important (PCI) criteria (Appendix C) using all post-baseline values. For each vital sign PCI criterion, the number and percentage of subjects who have a vital sign value meeting the criteria will be summarized. Listings will be provided to summarize subject-level vital sign data for subjects meeting PCI criteria.

#### 10.5 Other Safety Analyses

ECG findings will be summarized for all time points (Baseline, Day 3, Day 6, Day 13, and end of study follow-up) using the investigator interpretation. The summaries will include the number and percentage of patients in the following categories:

- Normal
- Abnormal Not Clinically Significant
- Abnormal Clinically Significant

Counts will be provided for the category "Interpretation not possible."

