9.3.3.8 Standard 12-lead ECG

A complete standard 12-lead ECG will be recorded in the supine position using a computerised ECG device at the time-points specified in the Schedule of Events (see **Appendix 1** and **Appendix 2**).

The following parameters will be calculated:

- heart rate,
- PR interval,
- QRS-interval,
- QT/ QTcF interval (uncorrected and corrected QT interval according to Fridericia's formulae).

All ECGs recorded will be read by a physician experienced in evaluating ECGs, providing an ECG diagnosis and overall assessment, including clinical significance and changes compare to screening. The data from this central reading will be used for the statistical analysis.

Any clinically significant abnormality on ECG will be checked by repeat ECG. Any clinically significant ECG abnormality that is confirmed by repeat ECG will be assessed in accordance with the instructions in Section 9.3.4 and may be considered to be an AE.

The triplicate ECG recordings at Screening for the purposes of assessing eligibility may be repeated only once. Triplicate ECGs will be performed at all time points, except at Day 3 in Part 1 when single ECGs will be performed.

Detailed instructions for recording and handling of the ECGs will be provided in the Study Operations Manual/SOPs.

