10.8 Statistical Analysis of Safety

All safety analyses will be performed on the Safety Population, which consists of all subjects who received at least one dose of IMP. Safety will be assessed by AEs, laboratory tests, vital signs, and ECG variables. Details of the analyses will be provided in the Statistical Analysis Plan.

AEs will be coded using the Medical Dictionary for Regulatory Activities (MedDRA). A TEAE is defined as an AE with an onset date that is after the first intake of IMP and no more than 30 days after the last intake of IMP. The number and percentage of subjects experiencing TEAEs will be tabulated using MedDRA system-organ class and preferred term, as well as by severity and by relationship to the IMP as assessed by the Investigator. Summaries of SAEs, deaths, AEs leading to discontinuation will also be provided.

For laboratory test and vital signs variables, mean change from baseline and percentage of subjects with on-treatment laboratory values of CTCAE 5.0 adapted scale grade 3 or 4 will be summarised.

10.9 Interim Analysis of Part 1 and DSMB Recommendation to Proceed to Part 2

Once subjects in Part 1 have completed or prematurely discontinued the study, up to and including nodulectomy at 6 months, a database lock for Part 1 database and an interim analysis of data from Part 1 will be conducted by the Sponsor and the randomisation code unblinded. The unblinded data will be reviewed by the Sponsor and the DSMB (see Section 13.3), for futility and risk/benefit ratio. Taking into account the recommendations of the DSMB, especially regarding the safety assessment of the data, the Sponsor will decide whether or not to proceed to Part 2, and with which dose regimens.

Selection of up to two acceptable/suitable doses / regimens for Part 2 will be based on analysis of all of available unblinded data from Part 1, including safety and tolerability of ABBV-4083 and ABBV-4083 + albendazole, *Wolbachia* depletion, disruption of embryogenesis and an exploratory surrogate marker, microfilaria *Wolbachia*, observed at Months 3 and 6.

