# 1.0 Introduction

This Statistical Analysis Plan (SAP) describes the statistical analyses of Part 1 only for ABBV-4083 Study B18-894/DNDi-TYL-01 "A Phase-II, Randomised, Double-blind, Parallel-group, Proof-of-concept Trial to investigate ABBV-4083 given for 7 or 14 Days or in combination with Albendazole in Subjects with *Onchocerca volvulus* Infection." Part 2 will have a separate clinical database with a separate SAP and database lock.

Part 1 of Study B18-894/DNDi-TYL-01 investigates the safety, tolerability, efficacy for duration-ranging and pharmacokinetics of ABBV-4083 with or without albendazole in subjects infected with *Onchocerca volvulus*.

The analyses of pharmacokinetic endpoints and their relationship to efficacy and safety endpoints will not be covered in this SAP.

The SAP will not be updated in case of administrative changes or amendments to the protocol unless the changes impact the analysis.

Unless noted otherwise, all analyses will be performed using SAS Version 9.4 (SAS Institute Inc., Cary, NC 27513) or later under the UNIX operating system.

All analyses in this SAP are consistent with what is described in the study protocol unless otherwise noted in Section 13.0.

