		• Section 9.5 For ophthalmological exam outcomes, added blurred vision and night blindness to summary of clinical grade and clarified that anterior uveitis would have separate grades for number of cell/field and flare). For summaries of change from baseline in ocular and skin exam, summary category of "similarity" was changed to "no change."
		• Section 10.2.2, Section 10.2.3, and Section 10.2.4 Clarified that summaries of treatment-emergent AEs based on relationship to study drug and of treatment- emergent AEs leading to discontinuation of study drug would be performed with study drug defined in 4 ways: ABBV-4083, albendazole, ABBV-4083 and/or albendazole, and ABBV-4083 and albendazole. The description of the summary of all deaths was clarified to include time periods.
		• Section 10.2.4 Added listings of all SAEs and all deaths.
		• Section 10.3 Deleted statement about including laboratory testing due to an SAE because SAE-related laboratory assessments are not collected in a format that can be summarized. Removed summary of creatinine clearance and added eGFR because eGFR is collected in the study and is more applicable to the study population. Removed summary of urinalysis data because only abnormal results are collected. Clarified that changes from baseline would be analyzed using ANOVA models. Provided more detail about the analyses related to normal range shift for laboratory parameters. Added separate summaries for a maximum of Grade 3 and a maximum of Grade 4 for graded laboratory parameters. Added an eDISH plot for AST versus bilirubin.
		• Section 10.4 Clarified that changes from baseline would be analyzed using ANOVA models. Clarified that
		evaluation of potentially clinically important criteria are to be assessed using all post-baseline values.

Version	Date	Summary
		• Section 10.5 Deleted Month 3 visit summary because ECG data are not collected at Month 3. Clarified that only investigator interpretation of ECG would be summarized and that percentages would be calculated using only interpretable tests.
		
 
Appendix A Added the protocol deviation categories.
 
Appendix B Clarified that any subject taking a prohibited medication will be documented as a protocol deviation.
 

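### SAP 10.5 takes the Part 1 ECG results from the investigator interpretation where protocol 9.3.3.8 names the central reading, and no summary of PR, QRS or QTcF is planned

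*SAP*

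**What the plan says.** Protocol 9.3.3.8 has every ECG read by a physician with ECG experience, "providing an ECG diagnosis and overall assessment, including clinical significance and changes compare to screening". It continues: "The data from this central reading will be used for the statistical analysis". The same section lists heart rate, PR, QRS and QT/QTcF as parameters to be calculated, and adds: "Triplicate ECGs will be performed at all time points, except at Day 3 in Part 1 when single ECGs will be performed".

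Protocol 10.8 includes ECGs in the safety assessment: "Safety will be assessed by AEs, laboratory tests, vital signs, and ECG variables". It leaves the details to the SAP. Its only specific commitment on continuous measures begins "For laboratory test and vital signs variables, mean change from baseline"; ECG is not named there.

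SAP 10.5 reads: "ECG findings will be summarized for all time points (Baseline, Day 3, Day 6, Day 13, and end of study follow-up) using the investigator interpretation". Its output is three categories (normal, abnormal without clinical significance, abnormal with clinical significance) plus a count of ECGs that could not be interpreted.

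SAP 1.0 gives a general assurance: "All analyses in this SAP are consistent with what is described in the study protocol unless otherwise noted in Section 13.0". The Section 13.0 entry for 10.5 says: "Clarified that only investigator interpretation of ECG would be summarized".

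**The concern.** Two current texts give different sources for the same table. If the readings differ in practice, the reported ECG categories would come from a source other than the one the protocol fixed, and a reader relying on SAP 1.0 would not learn this from an entry worded as a clarification.

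The second point is content. A three-category table cannot show a mean shift in an interval, and it hides the size of any outlier that the reader considers clinically unimportant. The sponsor and the DSMB use the unblinded Part 1 results to decide whether to start Part 2 and with which regimens. ECGs are taken 1-2 hours after dosing (protocol Appendix 1, footnote 15), which overlaps the Phase I time of peak concentration of about 1.5 to 2 hours (protocol 2.3.1.2). The recordings are therefore well timed to show an interval effect, but nothing planned would display it.

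**Working it through.** **1. Data source.**

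| | Protocol 9.3.3.8 | SAP 10.5 |
|---|---|---|
| Reader | physician with ECG experience; called a central reading | investigator |
| Output | diagnosis, overall assessment including clinical significance; heart rate, PR, QRS, QT/QTcF | three categories and a count of uninterpretable tests |
| Basis for analysis | the central reading | the investigator interpretation |

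Neither text is superseded. Protocol 10.8 delegates details of the safety analyses to the SAP, but 9.3.3.8 had already settled the data source.

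**2. Disclosure.** The Section 13.0 entry makes the choice visible. It mentions neither the protocol nor the central reading, and gives no reason. Other entries do give reasons: the Month 3 ECG summary was dropped because no ECG is taken then, and the PCR endpoint was changed because of data availability.

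**3. Intervals.** SAP 3.4 lists the 12-lead ECG as a safety endpoint. SAP 10.5 contains no interval value, and Appendix C covers laboratory grades (Table C-1) and vital signs (Table C-2) only. Heart rate is covered as a vital sign in SAP 10.4. PR, QRS and QT/QTcF have no summary, change from baseline or threshold. SAP 10.5 also does not say how three recordings become one category per visit.

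**4. How much planned data this covers** (30 per arm, no missing data).
- Subject-visits on ABBV-4083: Day 3, 4 × 30 = 120; Day 6, 4 × 30 = 120; Day 13, Arm B only, 30. Total 270.
- Recordings: 120 × 1 + 120 × 3 + 30 × 3 = 570.
- Values of PR, QRS and QTcF: 270 × 3 = 810.

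**5. Albendazole co-dosing.** The protocol describes no human ECG data with the two drugs together. Arm C takes both on Days 0-6, so same-day co-dosing gives 30 × 2 = 60 subject-visits and 60 × 3 = 180 values. Arm D's last albendazole dose is on Day 2, and its Day 3 ECG falls 24 + 1 to 24 + 2 = 25-26 hours later. Protocol 3.5.2.2 gives albendazole sulfoxide a half-life of 8-12 hours. Assuming simple first-order decay, the fraction left is 0.5^(26/8) = 0.105 to 0.5^(25/12) = 0.236, roughly 11-24%. Arm D on Day 3 is thus not co-dosed that day but may be partly co-exposed.

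**6. Which contrast answers what.** Arm E takes albendazole on Days 3 and 6. Then C v E shows ABBV-4083 added to albendazole, while A v E sets one drug against the other. Only C v A shows albendazole added to 7 days of ABBV-4083.

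**7. Precision of such tables (illustration only).** The documents give no SD for QTcF change; 10-20 ms is assumed.
- Half-width = t(0.975, n1 + n2 − 2) × SD × √(1/n1 + 1/n2).
- 30 v 30: 5.17, 7.75 and 10.34 ms for SD 10, 15 and 20.
- 120 v 30 (A-D v E): 4.03, 6.05 and 8.07 ms.
- If no subject exceeded a given cut-off, the exact 95% upper limit is 1 − 0.025^(1/n): 3.03% for n = 120 and 11.57% for n = 30.

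**The case against.** **The two readings may be one.** Protocol 9.3.3.8 does not say that the reader is outside the centre, and protocol 13.1 lets the term investigator cover a qualified delegate there. No passage describes two parallel readings. This stands. A reader might infer that the table will certainly rest on the wrong reading; the documents support only that it may.

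**The choice was disclosed.** SAP 1.0 asks for departures to be noted in Section 13.0, and the choice is noted there. This stands against any suggestion of concealment. It does not settle the matter, because the entry gives no sign that the protocol says something else.

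**Interval summaries were never promised.** Protocol 10.8 specifies mean change for laboratory tests and vital signs only. Clinically significant abnormalities are tabulated and may become AEs, and PK-safety relationships lie outside this SAP. All of this is correct. A reader might infer a breach of the protocol; there is none. There is a gap between naming ECG variables as a safety assessment and summarising none of the intervals.

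**Earlier evidence is reassuring.** Dog telemetry showed no ECG effect (protocol 2.2.2). Phase I showed no apparent relation between concentration and QTcF, with 78 subjects exposed and single doses up to 1000 mg. This lowers the expected yield, but that evidence is for ABBV-4083 alone.

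**The counts do not measure harm.** Agreed. They show how much planned data lacks a summary. The effect of using one reading rather than another cannot be sized from the documents.

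**Conclusion.** The inconsistency over the data source is real and should be resolved. Its practical effect is unknown, because the documents do not say whether the two readings differ. The missing interval summaries are a gap worth closing: 810 planned on-treatment values at full enrolment, 180 of them under same-day co-dosing in Arm C. That Part 1 co-exposure data can come from Arm C alone would be too strong an inference, given possible residual metabolite in Arm D on Day 3. Nor do the documents indicate an ECG signal. The primary efficacy conclusion is untouched. The conclusion rests on comparing the texts and does not depend on the assumed SD or on the decay calculation.

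**What to change.** 1. In SAP 10.5, take the ECG categories from the central reading, as protocol 9.3.3.8 states. If the investigator reading is kept, record it in Section 13.0 as a departure from 9.3.3.8 with the reason, or state that the two readings are the same. Say how a triplicate yields one category per visit.

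2. Add descriptive summaries of QTcF, PR and QRS by arm and visit, using the mean of the triplicate where one is taken, with change from baseline and 95% CI in the style of SAP 10.4.
   - Show each arm v Arm E, and C v A at Days 3 and 6.
   - Pool A-D v E only at Days 3 and 6. At Day 13 only Arm B is still on ABBV-4083, so show B v E as the on-treatment contrast.
   - Present Arm C as the arm with same-day co-dosing. Show Arm D on Day 3 as well, noting possible residual albendazole sulfoxide.

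3. Optionally, add counts of subjects above descriptive cut-offs. The limits in exclusion criterion 10 (PR 240, QRS 120, QTcF 450 msec) are one available reference for reporting. They are eligibility limits, not an on-treatment clinical rule.

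The cost is SAP wording and a few descriptive tables from data the protocol already requires. No procedures, visits or subjects are added.

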# 11.0 Interim Analyses

No interim analysis is planned for Study B18-894/DNDi-TYL-01 Part 1.

#### 11.1 Data and Safety Monitoring Board

An independent Data and Safety Monitoring Board (DSMB) will be established by the Sponsor in accordance with ICH guidelines. The DSMB will be composed of a minimum of three members, including at least one medically qualified disease expert and a statistician, in accordance with any requirements specified by the regulatory authorities. The composition, roles, and responsibilities of the DSMB will be described in detail in a separate DSMB charter.

During the study, the DSMB will review reports about enrolment, subject discontinuation, subject demographic, and safety data, including serious and non-serious AEs and other safety parameters, cases of exposure during pregnancy and outcomes, PK results (only drug concentration data), concomitant treatments, as well as ad-hoc requests if deemed necessary by the Sponsor and in line with the DSMB charter.

The DSMB will also review and evaluate, at intervals and as defined in the DSMB charter, the progress, scientific validity, data integrity, and the safety of the clinical trial, and make recommendations to the Sponsor about whether to continue, modify or terminate the trial. The DSMB may also request unblinding of certain subject(s), e.g., in case of a major safety concern, but only if absolutely necessary, and always in accordance with the DSMB Charter.

In addition, a Safety Review Committee (SRC) will be appointed with a minimum of three Sponsor representatives, including at least one medically qualified person, and the Investigators. The exact composition, roles, and responsibilities of the SRC will be described in a separate SRC Charter.

Once at least 15 subjects have been treated in each of the five arms, the SRC will review safety results separately for each arm every 2 weeks and evaluate causality. If > 10% of the subjects in any arm meet any of the toxicity criteria, the SRC will inform the DSMB. The DSMB will review the reports and make non-binding recommendations regarding halting enrolment into Arms A, B, C or D and opening enrolment in appropriate arms with the lower dose of ABBV-4083.

Both the Sponsor and the DSMB will review the final unblinded analyses of Study B18-894/DNDi-TYL-01 Part 1. The DSMB will provide a non-binding recommendation to the Sponsor about whether to proceed to Part 2 and with which dose regimens.

# 12.0 Overall Type-I Error Control

Since Study B18-894/DNDi-TYL-01 Part 1 is for proof of concept, no multiplicity adjustment for alpha spending will be used.

# 13.0 Version History

Version	Date	Summary
1.0	02 Nov 2021	Original version
2.0	24 Mar 2023	
 
Section 1.0 Noted that analyses inconsistent with the protocol are noted in Section 13.0.
 
Section 2.3 Administrative clarification of randomization was made.
 

#### Table 2.SAP Version History Summary

Version	Date	Summary
		• Section 3.2 and Section 9.4.2 Secondary endpoint of status of each live female adult worm as without Wolbachia assessed by PCR at Month 6 has been changed to status of each nodule containing at least one live female adult worm as without Wolbachia assessed by PCR at Month 6 due to a change in PCR data availability.
		• Section 3.4 For safety endpoints, removed physical, skin, and ophthalmological examination findings since they are summarized as the secondary efficacy endpoints.
		• Section 3.4 For safety endpoints, removed urine analysis because only abnormal results are collected.
		• Section 4.0 and Section 10.1 Updated safety analysis arms to be determined by the subject's randomized arm to align with treatment regimens under study.
		• Section 5.0 Subject disposition summary for completed protocol-specified treatment, prematurely discontinued study drug, reason for discontinuation of study drug, interruption of study drug, and reason for interruption of study drug were clarified to include summaries by study drug.
		• Section 6.0 Study drug duration categorical summary was updated to add the category of "> 14 days."
		• Q1, Q3 were added to all numerical summaries that included calculation of the median.
		• Section 7.1 and Section 9.6 For demographics and baseline characteristics, categories for number of operable sites with onchocercomata, number of palpated nodules, and number of previous ivermectin rounds were updated to be 0, 1, >1. Also, number of years resident in endemic area was added, and for summary of symptoms of onchocerciasis disease, "other" category was removed.
		• Section 7.3 Summaries of prior and concomitant procedures were removed because they are collected as text fields. Anthelmintic medications taken prior to the start of study drug were removed from the summary of concomitant medications because by definition these medications were only taken prior to start of study drug.
		• Section 8.0 and Section 9.2 Clarified the conditions which lead to data imputation.
		• Section 9.1 Clarified that no adjustment for multiple comparisons would be made.

Version	Date	Summary
		• Section 9.5 Clarified that the decline in number of Wolbachia , as assessed by PCR, would be assessed using the ratio of PCR copy number of Wolbachia signal to PCR copy number of worm signal.
		• Section 9.5 For ophthalmological exam outcomes, added blurred vision and night blindness to summary of clinical grade and clarified that anterior uveitis would have separate grades for number of cell/field and flare). For summaries of change from baseline in ocular and skin exam, summary category of "similarity" was changed to "no change."
		• Section 10.2.2, Section 10.2.3, and Section 10.2.4 Clarified that summaries of treatment-emergent AEs based on relationship to study drug and of treatment- emergent AEs leading to discontinuation of study drug would be performed with study drug defined in 4 ways: ABBV-4083, albendazole, ABBV-4083 and/or albendazole, and ABBV-4083 and albendazole. The description of the summary of all deaths was clarified to include time periods.
		• Section 10.2.4 Added listings of all SAEs and all deaths.
		• Section 10.3 Deleted statement about including laboratory testing due to an SAE because SAE-related laboratory assessments are not collected in a format that can be summarized. Removed summary of creatinine clearance and added eGFR because eGFR is collected in the study and is more applicable to the study population. Removed summary of urinalysis data because only abnormal results are collected. Clarified that changes from baseline would be analyzed using ANOVA models. Provided more detail about the analyses related to normal range shift for laboratory parameters. Added separate summaries for a maximum of Grade 3 and a maximum of Grade 4 for graded laboratory parameters. Added an eDISH plot for AST versus bilirubin.
		• Section 10.4 Clarified that changes from baseline would be analyzed using ANOVA models. Clarified that
		evaluation of potentially clinically important criteria are to be assessed using all post-baseline values.

Version	Date	Summary
		• Section 10.5 Deleted Month 3 visit summary because ECG data are not collected at Month 3. Clarified that only investigator interpretation of ECG would be summarized and that percentages would be calculated using only interpretable tests.
		
 
Appendix A Added the protocol deviation categories.
 
Appendix B Clarified that any subject taking a prohibited medication will be documented as a protocol deviation.
 

		• Appendix C Removed creatinine clearance from table and added eGFR because eGFR is collected in the study and is more applicable to the study population. Revised albumin criteria to use units of g/dL. Updated grade definitions for ALT, AST, ALP, and bilirubin to match CTCAE v5.

